### 8.4.2 Trial Suspension Rule

A trial suspension rule will be applicable during the entire trial. This rule is met if a subject vaccinated with CVnCoV experiences an SAE considered related to the trial vaccine by the Investigator or Sponsor.

If this rule is met, enrollment and vaccination with CVnCoV will be suspended within 24 hours after reporting to the trial team. An ad-hoc Data Safety Monitoring Board (DSMB) meeting will be held to review all safety data per the DSMB charter. Depending on the DSMB assessment of the benefit-risk ratio, including the relationship of the SAE to the trial vaccine, enrollment and vaccination with CVnCoV might be temporarily halted and only be re-started upon approval by the DSMB and competent authority.

#### 8.4.3 Justification for Dose

Two provisional CVnCoV dose levels (6 and 12 µg) will be evaluated. Based on favorable immunogenicity data and tolerable safety/reactogenicity data administered with 12 µg in Trial CV-NCOV-001, the DSMB endorsed the decision to implement the 12 µg dose in this phase 2a trial. Refer to the Investigator's Brochure for an overview of the CVnCoV non-clinical data.

Additional higher, lower, and/or intermediate dose levels might be evaluated depending on the outcomes of Trial CV-NCOV-001, as well as data from Trial CV-NCOV-002. Identification of immunogenic dose levels with lower mRNA content might be of particular importance for efficient vaccination in a worldwide viral outbreak setting

#### 8.4.4 End of Trial Definition

A subject is considered to have completed the trial when he/she has completed all visits applicable for the group to which he/she was randomized/assigned to at trial entry.

End of Trial is defined as the point at which the last subject has completed the last visit or last phone contact.

### 8.5 Sample Size Considerations

Due to the exploratory nature of this trial, only descriptive statistics will be used. No confirmatory statistical inference will be performed.

#### 8.5.1 Sample Size Determination

The sample size of the trial ensures that sufficient safety and immunogenicity data will be available for the selected CVnCoV dosage(s) prior to initiation of Phase 3 clinical trials. Approximately 200 subjects will be enrolled in the initial phase to investigate different dose levels and 20 subjects as control. Furthermore, 440 subjects will be enrolled in an expansion phase (400 will receive CVnCoV and 40 the active control). Overview in Table 2.

**Table 2**      **Sample Size**

Open-label	Randomized										
	Dose escalation a	Group 1	Group 2	Group 3	Group 4	Expansion Age 18-60	Expansion Age >60	Total CVnCoV	Group 5 Active control Age 18-60	Group 6 Active control Age >60	Expansion Active control Age ≥18
		6 µg Age 18-60	6 µg Age >60	12 µg Age 18-60	12 µg Age >60						
4	11	12c	90	90	200	200	603	10b	10b	40	

a. Only if the dose level was previously untested.

b. Includes 1 control subject from Group 1 and 1 control subject from Group 2.

c. Includes the 4 subjects from the dose escalation.

The trial is designed to provide a reasonable precision for an estimate of the number of subjects with seroconverting for nCoV spike protein antibodies and an acceptable rate of Grade 3 adverse reactions (ARs). Table 3 provides the estimate and 95% credibility interval for the observed numbers of subjects with seroconverting for nCoV spike protein antibodies for different sample sizes assuming a Beta (1.9,0.1) prior for seroconverting for nCoV spike protein antibodies and a Beta (0.5,1.5) prior for Grade 3 adverse reactions.

**Table 3 Estimate of Number of Subjects with Seroconverting for nCoV Spike Protein Antibodies and 95% Credibility Interval**

Rate (%)	Sample Size					
	90		200		603	
	N	95% CI	N	95% CI	N	95% CI
80	72	80.3 (71.7 - 87.7)	160	80.1 (74.4 - 85.3)	482	80 (76.7 - 83.1)
85	76	84.7 (76.7 - 91.2)	170	85.1 (79.9 - 89.7)	513	85 (82.2 - 87.8)
90	81	90.1 (83.3 - 95.3)	180	90 (85.6 - 93.8)	543	90.1 (87.6 - 92.3)
95	86	95.5 (90.5 - 98.7)	190	95 (91.6 - 97.6)	573	95 (93.2 - 96.6)
100	90	99.9 (98.9 - 100)	200	100 (99.5 - 100)	603	100 (99.8 - 100)

Cl: credibility interval; N: subjects with seroconverting for nCoV spike protein antibodies

Table 4 provides probabilities (in %) that the following 2 conditions are simultaneously met for assumed true adverse reaction rates and for assumed true rates with seroconverting for nCoV spike protein antibodies and for different sample sizes:

- there is a  $\geq 80\%$  probability that the true rate of Grade 3 AR(s) is  $\leq 33\%$ , and
- there is a  $\geq 90\%$  probability that the true rate of subjects seroconverting for nCoV spike protein antibodies  $> 95\%$ .

For example, for a sample size of 200, assuming a true AR rate of 20% and a true rate of subjects seroconverting for nCoV spike protein antibodies of 97.5%, the 2 conditions are met with a probability of 76%.

**Table 4 Probabilities (in %) for Assumed True Adverse Reaction Rates and for Assumed True Rates of Subjects with Seroconverting for nCoV Spike Protein Antibodies and Different Sample Sizes**

True adverse reaction rate (%)	Sample Size								
	90			200			603		
	True rate of subjects with seroconverting for nCoV spike protein antibodies (%)			True rate of subjects with seroconverting for nCoV spike protein antibodies (%)			True rate of subjects with seroconverting for nCoV spike protein antibodies (%)		
True adverse reaction rate (%)	95	97.5	100	95	97.5	100	95	97.5	100
5	17	61	100	12	76	100	10	98	100
10	17	61	100	12	76	100	10	98	100
15	17	61	100	12	76	100	10	98	100
20	16	60	98	12	76	100	10	98	100
25	14	51	83	12	73	96	10	98	100
30	8	28	46	7	41	54	8	78	79
35	2	8	13	1	6	8	0	3	3

## 8.6 Randomization

The first part of the trial will be conducted with 4 CVnCoV groups versus 2 active controls. In the initial phase, subjects will be randomized according to a 10:1 ratio to receive CVnCoV or the active control in an observer-blinded manner.

Subjects in the expansion cohorts will be randomized according to a 10:1 ratio to receive either the selected dose of CVnCoV or the active control in an observer-blinded manner; 200 subjects per age category will receive CVnCoV and 20 subjects will receive the active control.

## 8.7 Blinding/Unblinding

The Sponsor and safety monitoring committees will be unblinded for data from the randomized groups, but will take appropriate measures to ensure subject blinding is kept at site level until database lock. Subjects may request to be unblinded in case they are eligible for an authorized/licensed SARS-CoV-2 vaccine.

## 8.8 Licensed/Authorized Vaccine

Since the efficacy results from Trial CV-NCOV-004 are available and all subjects in this trial are currently eligible to receive a licensed/authorized vaccine, all subjects in this trial will be unblinded.

Each subject will be informed by the study physician of the available efficacy results from Trial CV-NCOV-004 and whether he/she received CVnCoV or an active control. All subjects will be asked to remain in the trial to allow safety follow-up. For details related to the censoring rules for the analysis see section 10.8.

## 9.0 Study Endpoints

The endpoints will be analyzed in all subjects, in subjects retrospectively SARS-CoV-2 seronegative at baseline, and in subjects retrospectively SARS-CoV-2 seropositive at baseline.

### 9.1 Primary Endpoints

The primary endpoints are stated in section 9.4.

### 9.2 Secondary Endpoints

The secondary endpoints are stated in section 9.4.

### 9.3 Exploratory Endpoints

The exploratory endpoints are stated in Section 9.4.

### 9.4 Estimands

ENDPOINTS (subject level)	ESTIMANDS (population level)
Primary Safety	

The frequencies, intensities, and duration of solicited local AEs on Day 1 and Day 29 and the following 7 days by dose and group.
 
The frequencies, intensities, duration, and relationship to trial vaccination of solicited systemic AEs on Day 1 and Day 29 and the following 7 days by dose and group.
 
The occurrence, intensity and relationship to trial vaccination of unsolicited AEs on each vaccination day and the following 28 days by dose and group.
 
The occurrence and relationship to trial vaccination of SAEs and AESIs throughout the trial.
	
Safety set. Subjects who were unblinded and/or received an authorized/licensed COVID-19 vaccine will be censored at the day after unblinding and/or vaccination receipt.
 
The number and percentage of subjects overall and by dose level:
 
Each solicited local AE within 7 days after each trial vaccination by intensity and overall.
 
Each solicited systemic AE within 7 days after each trial vaccination by intensity, by relationship to trial vaccine and overall.
 
The mean duration in days by group with standard deviation of solicited AEs (within the solicited period, total duration).
 
At least 1 unsolicited AEs, at least 1 grade unsolicited AEs and each unsolicited AEs by SOC/PT occurring within 28 days after each trial vaccination and overall by causal relationship to trial vaccine and overall.
 
At least 1 SAE, or at least 1 AESI to vaccine overall by causal relationship to trial vaccine and overall.

ENDPOINTS (subject level)	ESTIMANDS (population level)
Primary Immunogenicity	
On Day 29 and Day 43 
 
The proportion of subjects seroconverting for SARS-CoV-2 spike protein antibodies, as measured by ELISA.
 
Individual SARS-CoV-2 spike protein-specific antibody levels in serum, as measured by ELISA.
 
Geometric mean titers (GMTs) of serum SARS-CoV-2 spike protein antibodies, as measured by ELISA.
 
The proportion of subjects seroconverting for SARS-CoV-2 neutralizing antibodies, as measured by an activity assay.
 
Individual SARS-CoV-2 neutralizing antibody levels in serum.
 
GMTs of serum SARS-CoV-2 neutralizing antibodies, as measured by an activity assay.
 
	Immunogenicity set. Subjects receiving an authorized/licensed COVID-19 vaccine during the course of the trial will be censored at the day after intake.  Sensitivity analysis: in addition, the primary immunogenicity analysis will be repeated for subjects who received dose 1 and dose 2 (and if eligible and received a booster dose at day 57 or day 180) of trial vaccine and for whom the baseline blood sample for immunogenicity assessment was seronegative and day 43 are available for analysis and no major protocol deviations expected to impact the immunogenicity outcomes. Subjects exposed to SARS-CoV-2 prior to the trial will be excluded. Subjects will be excluded at the time point they have been exposed to SARS-CoV-2.  Estimate of subjects seroconverted (SARS-CoV-2 spike protein-specific antibodies) with 95% credibility interval using prior beta(1.9, 0.1)  Number and percentage with exact 95% confidence intervals of subjects for who a seroconversion is observed (SARS-CoV-2 spike protein-specific antibodies)  Geometric mean of Fold Change from baseline with 95% CI (SARS-CoV-2 spike protein antibodies)  Estimate of subjects seroconverted (SARS-CoV-2 neutralizing antibody levels in serum) with 95% credibility interval using prior beta(1.9, 0.1)  Number and percentage with exact 95% confidence intervals of subjects for who a seroconversion is observed (SARS-CoV-2 neutralizing antibody levels in serum)  Geometric mean of Fold Change from baseline with 95% CI (SARS-CoV-2 neutralizing antibody levels in serum)
Secondary Safety	
	Safety set. Applicable for subjects who received a booster dose at day 57 or day 180. Subjects unblinded and/or received an authorized/ licensed vaccine during the course of the trial will be censored at the day after unblinding or receipt of authorized/ licensed vaccine (whichever is earlier).

ENDPOINTS (subject level)	ESTIMANDS (population level)

 
The frequencies, intensities, and duration of solicited local AEs on the day of the booster administration and the following 7 days by group.
 
The frequencies, intensities, duration, and relationship to trial vaccination of solicited systemic AEs on the day of the booster administration and the following 7 days by group.
 
The occurrence, intensities and relationship to trial vaccination of unsolicited AEs on the day of the booster administration and the following 28 days by group.
 
	
The number and percentage of subjects by group reporting:
 
 
Each solicited local AE within 7 days after each trial booster vaccination by intensity and overall
 
Each solicited systemic AE within 7 days after each trial booster vaccination by intensity, by relationship to trial vaccine and overall.
 
At least 1 unsolicited AEs, at least 1 grade 3 unsolicited AEs and each unsolicited AEs by SOC/PT occurring within 28 days after each trial booster vaccination and overall by causal relationship to trial vaccine and overall
 
The mean duration in days by group with standard deviation of solicited AEs (within the solicited period, total duration).
 

Secondary Immunogenicity	

Day 57 (only for subjects receiving the booster dose on Day 57),
 
Day 85 (only for subjects receiving the booster dose on Day 57),
 
Day 180 (only for subjects receiving the booster dose on Day 57 or Day 180),
 
Day 208 (only for subjects receiving the booster dose on Day 180), and
 
Day 393 (only for subjects receiving the booster dose on Day 180):
 
 
The proportion of subjects seroconverting for SARS-CoV-2 spike protein antibodies, as measured by ELISA.
 
Individual SARS-CoV-2 spike protein-specific antibody levels in serum, as measured by ELISA.
 
GMTs of serum SARS-CoV-2 spike protein antibodies, as measured by ELISA.
 
	
Immunogenicity set. Applicable for subjects who received a booster dose at day 57 or day 180. Subjects receiving an authorized/licensed COVID-19 vaccine during the course of the trial will be censored at the day after intake.
 
Sensitivity analysis: In addition, the secondary immunogenicity endpoint will be repeated for subjects who received dose 1 and dose 2 (and if eligible and received a booster dose at day 57 or day 180) of trial vaccine and for whom the baseline blood sample for immunogenicity assessment and day 43 are available for analysis and no major protocol deviations expected to impact the immunogenicity outcomes. Subjects receiving an authorized/ licensed vaccine during the course of the trial will be censored at the day after receiving the authorized/ licensed vaccine. Subjects exposed to SARS-CoV-2 prior to the trial will be excluded. Subjects will be excluded at the time point they have been exposed to SARS-CoV-2.
 
Estimate of subjects seroconverted (SARS-CoV-2 spike protein-specific antibodies) with 95% credibility interval using prior beta(1.9, 0.1)
 
Number and percentage with exact 95% confidence intervals of subjects for who a seroconversion is

ENDPOINTS (subject level)	ESTIMANDS (population level)

 
The proportion of subjects seroconverting for SARS-CoV-2 neutralizing antibodies, as measured by an activity assay.
 
Individual SARS-CoV-2 neutralizing antibody levels in serum, as measured by an activity assay.
 
 
GMTs of serum SARS-CoV-2 neutralizing antibodies, as measured by an activity assay.
	
observed (SARS-CoV-2 spike protein-specific antibodies)
 
Geometric mean of Fold Change from baseline with 95% CI of SARS-CoV-2 spike protein antibodies
 
Estimate of subjects seroconverted (SARS-CoV-2 neutralizing antibody levels in serum) with 95% credibility interval using prior beta(1.9, 0.1)
 
Number and percentage with exact 95% confidence intervals of subjects for who a seroconversion is observed (SARS-CoV-2 neutralizing antibody levels in serum)
 
Geometric mean of Fold Change from baseline with 95% CI (SARS-CoV-2 neutralizing antibody levels in serum)

Exploratory	

Innate immune response
 
On Day 1 and Day 2 in a subset of subjects:
 
 
Serum cytokine concentrations, including but not limited to IFN-<math>\alpha</math>, IFN-<math>\gamma</math>, IL-6, chemokine ligand (CCL) 2, and IFN-<math>\gamma</math>-induced protein 10 (IP-10).
 
 
CMI response
 
On Day 1, Day 29, and Day 43 in peripheral blood mononuclear cells (PBMCs) in a subset of subjects:
 
 
The frequency and functionality of SARS-CoV-2 spike-specific T-cell response after antigen stimulation.
 
	
Immunogenicity set.
 
A subset of subjects (approximately 20 subjects per CVnCoV group). Subjects receiving an authorized/licensed COVID-19 vaccine during the course of the trial will be censored at the day after intake.
 
Minimum, Q1, Median, Q3, Mean and change from baseline with 95% CI.
 
Immunogenicity set.
 
A subset of subjects (approximately 20 subjects per CVnCoV group). Subjects receiving an authorized/licensed COVID-19 vaccine during the course of the trial will be censored at the day after intake. The CMI data will be listed.


Evaluation of infection
 
 
Number of subjects with virologically-confirmed SARS-CoV-2 infection as measured by RT-PCR.
 
	
Subjects who were unblinded and/or received an authorized/licensed COVID-19 vaccine will be censored at the day after unblinding and/or vaccination receipt. Excluding subjects who had a COVID-19 infection at baseline.
 
Safety set.
 
The number and percentage of subjects by group at baseline and by post-baseline time points with a positive RT-PCR result

ENDPOINTS (subject level)	ESTIMANDS (population level)
PCR at clinically determined time points throughout the trial. 
 
Number of subjects with asymptomatic SARS-CoV-2 infection as measured by serology at predefined time points.
 
	Immunogenicity set. The number and percentage of subjects by group at baseline and post-baseline with a positive RT-PCR result and/or infection defined by SARS-CoV-2 N-antigen and no COVID-19 symptoms.

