4.1.1 Primary

- To evaluate the safety and reactogenicity profile after 1 and 2 dose administrations of CVnCoV at different dose levels.
- To evaluate the humoral immune response after 1 and 2 dose administrations of CVnCoV.

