4.2.1 Primary

- The frequencies, intensities, and duration of solicited local AEs on Day 1 and Day 29 and the following 7 days by dose and group.
- The frequencies, intensities, duration, and relationship to trial vaccination of solicited systemic AEs on Day 1 and Day 29 and the following 7 days by dose and group.
- The occurrence, intensities and relationship to trial vaccination of unsolicited AEs on Day 1 and Day 29 and the following 28 days by dose and group.
- The occurrence and relationship to trial vaccination of SAEs and AESIs throughout the trial.

On Day 29 and Day 43:

- The proportion of subjects seroconverting for SARS-CoV-2 spike protein antibodies, as measured by ELISA.

- Individual SARS-CoV-2 spike protein-specific antibody levels in serum, as measured by ELISA.
- Geometric mean titers (GMTs) of serum SARS-CoV-2 spike protein antibodies, as measured by ELISA.
- The proportion of subjects seroconverting for SARS-CoV-2 neutralizing antibodies, as measured by an activity assay.
- Individual SARS-CoV-2 neutralizing antibody levels in serum.
- GMTs of serum SARS-CoV-2 neutralizing antibodies, as measured by an activity assay.

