4.2.2 Secondary

- The frequencies, intensities, and duration of solicited local AEs on the day of the booster administration and the following 7 days by group.
- The frequencies, intensities, duration, and relationship to trial vaccination of solicited systemic AEs on the day of the booster administration and the following 7 days by group.
- The occurrence, intensities and relationship to trial vaccination of unsolicited AEs on the day of the booster administration and the following 28 days by group.

On Day 57 (only for subjects receiving the booster dose on Day 57), Day 85 (only for subjects receiving the booster dose on Day 57), Day 180 (only for subjects receiving the booster dose on Day 57 or Day 180), Day 208 (only for subjects receiving the booster dose on Day 180), and Day 393 (only for subjects receiving the booster dose on Day 180):

- The proportion of subjects seroconverting for SARS-CoV-2 spike protein antibodies, as measured by ELISA.
- Individual SARS-CoV-2 spike protein-specific antibody levels in serum, as measured by ELISA.
- GMTs of serum SARS-CoV-2 spike protein antibodies, as measured by ELISA.
- The proportion of subjects seroconverting for SARS-CoV-2 neutralizing antibodies, as measured by an activity assay.
- Individual SARS-CoV-2 neutralizing antibody levels in serum.
- GMTs of serum SARS-CoV-2 neutralizing antibodies, as measured by an activity assay.

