### 7.1 Primary Objectives

- To evaluate the safety and reactogenicity profile after 1 and 2 dose administrations of CVnCoV at different dose levels.
- To evaluate the humoral immune response after 1 and 2 dose administrations of CVnCoV.

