## 10.5 Adverse Events (AEs)

An AE is any untoward medical occurrence in a subject or clinical investigation subject administered a pharmaceutical product and which does not necessarily have a causal relationship with this vaccination.

For outputs presenting occurrence of AEs for a defined period after a dose, the following distinctions are made if not otherwise stated; by any dose, dose 1, dose 2 and booster at day 57 and day 180. Any dose is defined as a subject who received at least one dose of either CVnCoV or active control.

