## 12.8 Adverse Events

The primary, secondary and exploratory endpoints will be analyzed overall, as well as in subjects retrospectively SARS-CoV-2 seronegative at baseline, and in subjects retrospectively SARS-CoV-2 seropositive at baseline as per the definition given in section 10.6.3.

Unsolicited AEs, including SAEs, and AESIs and solicited AE integrated to or recorded on the CRF will be coded using MedDRA Version 24.0 or higher, by SOC and PT.

If not stated otherwise, all summaries of unsolicited AEs will also include relevant solicited AEs.

For outputs presenting occurrence of AEs for a defined period after a dose, the following distinctions are made if not otherwise stated; by any dose, dose 1, dose 2 and booster at day 57 and day 180. Any dose is defined as a subject who received at least one dose of either CVnCoV or active control.

In general, percentages will be based on the number of subjects in the respective analysis set. In summary tables for AEs after the second or booster vaccination, percentages will be based on the number of subjects in the respective analysis set who received the second, or booster vaccination as applicable.

The primary and secondary safety endpoints will be analyzed using the safety set.

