## 12.8.2 Analysis Solicited AEs

The following summaries of solicited AEs within 7 days after each trial vaccination and within 7 days after any trial vaccination will be provided:

- Summary of solicited AEs, local AEs and systemic AEs, overall and by maximum grade
  - will also be presented by sex (female/male) for any dose, dose 1, dose 2 and booster dose regardless of retrospective serology status at baseline.
- Occurrence of local AEs, overall and by maximum grade
- Occurrence of systemic AEs, overall and by maximum grade
- Occurrence of related systemic AEs, overall and by maximum grade (mild / moderate / severe)
- Duration (days) of solicited AEs, overall and for grade 3 events
- Duration (days) of local AEs, overall and for grade 3 events
- Duration (days) of systemic AEs, overall and for grade 3 events
- Duration (days) of related systemic AEs, overall and for grade 3 events
- Daily summary of local AEs (only for each dose)
- Daily summary of systemic AEs (only for each dose)
- Daily summary of related systemic AEs (only for each dose)
- Summary of time of onset (Day) for grade 3 solicited AEs, any solicited AEs, local, systemic AEs, and related systemic AEs
- Time of onset (Day) of local AEs
- Time of onset (Day) of systemic AEs
- Time of onset (Day) of related systemic AEs
- Number and percentage of subjects with solicited Grade 3 adverse reaction(s) or SAEs considered as related to the trial vaccine according to the Investigator with the 95% credibility interval based on the Beta (0.5, 0.5) prior distribution for each dose level and dose will be calculated and summarized.
- Individual solicited local and systemic adverse events will be displayed in by-subject figures
- Individual grade 3 solicited local and systemic adverse events will be presented in a figure.

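### The SAP's primary unsolicited AE window silently widens to every vaccination, and its pooled any-dose AE summaries count booster periods that only some 12 µg subjects have

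*SAP*

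**What the plan says.** The primary safety objective in Protocol 4.1.1 is "To evaluate the safety and reactogenicity profile after 1 and 2 dose administrations of CVnCoV at different dose levels"; SAP 7.1 repeats it. Protocol 4.2.1 accordingly sets the primary unsolicited endpoint as "unsolicited AEs on Day 1 and Day 29 and the following 28 days by dose and group". Events after the booster form a secondary endpoint in Protocol 4.2.2: "unsolicited AEs on the day of the booster administration and the following 28 days by group". The version 2.0 entries in Protocol Appendix 12 give the reason for this wording: primary safety is assessed after the primary doses, and secondary safety after the booster.

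SAP 9.4 keeps Day 1 and Day 29 for the two primary solicited endpoints but writes "unsolicited AEs on each vaccination day and the following 28 days by dose and group" for unsolicited AEs. Its primary estimand column refers to each trial vaccination for both kinds of AE. SAP 6.1 lists changes from the protocol and does not mention this one.

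AE outputs for a defined period after a dose are presented "by any dose, dose 1, dose 2 and booster at day 57 and day 180" (SAP 12.8). The pooled category is defined thus: "Any dose is defined as a subject who received at least one dose of either CVnCoV or active control" (SAP 10.5, repeated in 12.8). SAP 12.8.1 uses it for unsolicited AEs. SAP 12.8.2 summarizes "solicited AEs within 7 days after each trial vaccination and within 7 days after any trial vaccination". Protocol 10.3.5.1 also plans an after-any-vaccination summary for solicited AEs.

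**The concern.** The primary question concerns a two-dose regimen, but the only pooled AE summaries run over every dose that a subject received. Boosters go to part of Groups 3 and 4 and to nobody else. A boosted subject therefore has a third window in which to become a subject with at least one AE, while 6 µg, control and expansion subjects have two. The resulting imbalance always raises the 12 µg percentage, and more so in subjects over 60 years, the population for whom the dose is being confirmed.

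The dose 1 and dose 2 tables do not replace the missing summary. The share of subjects with an event after either dose cannot be recovered from two marginal percentages: with 20% after each dose, it could lie anywhere from 20% (the same subjects) to 40% (no overlap).

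The SAP deals with the same problem for primary immunogenicity. Section 12.9.1 censors measurements after the booster and analyzes boosted subjects separately. Primary safety has no counterpart.

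**Working it through.** **Inputs** (planned numbers, Protocol Table 2, Protocol Table 5 and SAP Tables 1 and 2). The CVnCoV total reproduces: 11 + 12 + 90 + 90 + 200 + 200 = 603. Boosters: Group 3, 30 of 90 on Day 180; Group 4, 30 of 90 on Day 57 and 30 of 90 on Day 180. None is planned for the 23 subjects at 6 µg, the 60 controls (20 + 40) or the 400 CVnCoV expansion subjects. SAP 12.0 presents the expansion cohorts together with the initial phase, so the 12 µg denominators are 290 per age group (90 + 200) and 580 overall.

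**Observation window.** The vaccination day plus 28 days, on nominal dates: two doses cover Days 1 to 57, or 57 days. A Day 57 booster extends this to Day 85 (+28). A Day 180 booster adds Days 180 to 208 (+29).

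| Display | Boosted | Mean unsolicited window (days) | Against 57 |
|---|---|---|---|
| 6 µg; control | 0/23; 0/60 | 57 | 0 |
| 12 µg pooled, 18-60 | 30/290 (10.3%) | 57 + 30×29/290 = 60.0 | +5% |
| 12 µg pooled, >60 | 60/290 (20.7%) | 57 + (30×28 + 30×29)/290 = 62.9 | +10% |
| 12 µg pooled, all ages | 90/580 (15.5%) | 57 + (30×28 + 60×29)/580 = 61.4 | +8% |
| Group 3 alone | 30/90 (33.3%) | 57 + 30×29/90 = 66.7 | +17% |
| Group 4 alone | 60/90 (66.7%) | 57 + (30×28 + 30×29)/90 = 76.0 | +33% |

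**Effect on the percentage with at least one event.** The documents give no AE rates for this trial, so the per-dose risk p is an assumption, taken as equal and independent across doses. Two doses give 1 − (1 − p)², and three give 1 − (1 − p)³. With a boosted fraction f, the any-dose figure rises by f × p(1 − p)².

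At p = 20%, two doses give 36.0% and three give 48.8%, a difference of 12.8 points:
- pooled 12 µg, >60: 36.0 + 0.207 × 12.8 = 38.6%
- pooled 12 µg, all ages: 36.0 + 0.155 × 12.8 = 38.0%
- Group 4 alone: 36.0 + 0.667 × 12.8 = 44.5%

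For p of 5%, 10%, 20%, 30% and 50%, the rise runs from 0.7 to 2.3 points (pooled, all ages) and from 0.9 to 3.0 points (pooled, >60). The expression p(1 − p)² peaks at p = 1/3 with 4/27, so under these assumptions the pooled >60 shift cannot exceed 0.207 × 4/27 = 3.1 points.

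**After the change.** With booster windows left out, planned exposure is two doses and 57 days in every group.

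**The case against.** Much of the defense stands.

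- A reader might infer that all primary safety tables are contaminated. They are not. Outputs are split by dose, and percentages after the second or booster dose use the recipients of that dose (SAP 12.8). The dose 1 and dose 2 tables contain no booster exposure.
- The SAP's stated definition of any dose does not mention boosters; it requires only at least one dose. That booster windows are counted is an inference, though a fair one, because nothing excludes them.
- For solicited AEs the pooled summary follows Protocol 10.3.5.1, so SAP 6.1 had nothing to declare there. A change to the SAP alone would create a new conflict.
- A reader might take the any-dose column for the trial's headline comparison. Neither document gives it that status, and both describe the trial as descriptive with no confirmatory inference.
- The comparators are small. At a 36% rate the approximate 95% half-width, 1.96√(0.36 × 0.64/n), is 20 points for the 23 subjects at 6 µg and 17 points for 30 controls in one age group. A shift of 2 or 3 points would not by itself carry a dose conclusion.

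Censoring at unblinding (SAP 9.4 and 10.8) is not a reliable answer. The SAP does not say that an open-label booster counts as unblinding, and if it did, the secondary booster safety endpoint would be largely empty.

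None of this removes the undeclared wording change for unsolicited AEs or supplies a two-dose pooled summary. The by-sex overall summary in SAP 12.8.1 is specified for any dose only, so there the affected column is the only one stated.

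**Conclusion.** The point holds for two things: the undeclared widening of the primary unsolicited endpoint, and the pooled AE columns. It does not extend to the per-dose tables. The size is modest: a 10% longer mean window in pooled 12 µg subjects over 60, and about 1 to 3 percentage points on the any-dose rate, always in the direction of 12 µg.

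The tempting larger figure, 44.5% against 36.0% in Group 4, applies only if results are shown by initial-phase group. The endpoint wording allows that, and Protocol 10.3.5.1 speaks of solicited summaries in each phase, but SAP 12.0 pools the phases.

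All the percentages are illustrative. They assume planned numbers, full compliance, no dropout, and an equal, independent risk at each dose. For a given per-dose risk they sit at the upper end: positive correlation within subjects shrinks the shift, and the individual stopping rules (Protocol 5.4.1) keep some reactors from being boosted. A higher risk after the booster than after the primary doses would work the other way. Severity is minor to moderate.

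**What to change.** 1. In SAP 9.4, restore Day 1 and Day 29 in the primary unsolicited endpoint, and limit the primary solicited and unsolicited estimands to dose 1 and dose 2.
2. In SAP 10.5, 12.8, 12.8.1 and 12.8.2, add an any-primary-dose summary (dose 1 or dose 2) and make it the primary pooled summary of solicited and unsolicited AEs, including the by-sex tables. Attribute events from the booster onward to the booster; SAP 10.5.3 already has a rule for unsolicited AEs on the booster day.
3. Keep the any-dose column as supportive, labelled as including boosters. Reconcile it with Protocol 10.3.5.1 or declare the difference in SAP 6.1.
4. Keep SAEs and AESIs reported throughout the trial for all subjects, with an added split before and after the booster. Their primary endpoint is trial-wide and the secondary safety endpoints have no SAE or AESI item, so moving booster-period events to the secondary tables would leave them without an endpoint.

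The cost is one flag in the AE dataset, a few extra table columns and some wording. No new data are needed and no event is dropped. A Day 57 booster given early in its visit window would close the dose 2 window slightly short of 28 days; a footnote can say so.
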